Prior to study start, within the Bariatric Surgery Center, we had managed 13 patients perioperatively on phentermine, topiramate, or the combination for weight stabilization/loss. The PI and primary mentor continue to manage many additional patients on topiramate and phentermine in the broader Lifestyle Medicine weight management program at Children's Colorado, and we have developed clinical guidelines for the use of these medications at CHCO. In our perioperative experience, these medications are generally very well-tolerated.

Given the current Food and Drug Administration labeling for each of the proposed study drugs, the PI has successfully obtained an Investigational New Drug Application (IND 142590) for this pilot study. The IND is active for the use of phentermine and immediate release topiramate in 12-24 year olds after bariatric surgery as defined in this research protocol. We will follow a data and safety monitoring plan (see page 12), which includes an appointed Safety Officer in conjunction with IRB approval and study launch.

IV. Research Methods

A. Outcome Measure(s):

Primary Aim 1:

Feasibility

• Protocol Implementation: recruitment, enrollment, randomization, and dropout rates

 Acceptability: Adherence to medication: Self-report by questionnaire, pill counts and urine amphetamine testing | *Tolerability to medication*: Self-report by questionnaire assessing effects, side effects, barriers to adherence, and standardized assessment of possible adverse effects by study staff

Secondary Aim 2:

· Weight, BMI

Secondary Aim 3:

- Manual blood pressure
- Fasting lipid panel: Total cholesterol, HDL, non-HDL, LDL, Triglycerides
- Alanine aminotransferase (ALT) as a surrogate for non-alcoholic fatty liver disease improvement
- Hemoglobin A1c (HbA1c)
- Dietary intake
- Resting metabolic rate
- Body composition and Bone density
- Eating behaviors
- Physical activity
- Quality of Life

B. Description of Population to be Enrolled:

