Fourteen patients (7/arm) followed in the Children's Hospital Colorado Bariatric Surgery Center who meet inclusion criteria: 12-24yo; s/p SG or RYGB; and at 6-12 months post bariatric surgery^a, have either a) not achieved mean expected weight loss based on national standards and still have at least class 1 obesity or b) remain severely obese (\geq 120% of 95%ile or BMI \geq 35kg/m2 for 12-17yo; BMI \geq 35kg/m2 for 18-24yo) will be randomized 1:1 to pharmacotherapy + SOC^b or placebo + SOC in double-blind fashion. Expected weight loss at 6, 9, and 12 months postoperatively will be defined as a \geq 26%, \geq 28%, and \geq 31% decrease in weight, respectively, from preoperative weight (within 1 week of surgery) as was observed in the Teen-LABS study.⁷

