the participant in advance of the informed assent discussion using REDCap's survey distribution tool. The eAssent form is designed to allow the participant to navigate forward and backward through the entire form and to access the form at a later time if desired. During the informed assent discussion, the potential participant's questions will be answered and at the end, the participant will verbally confirm they agree to be in the study. Because there can only be one signature ("certifier") for each REDCap eAssent form, there are separate REDCap eAonsent forms for the adolescent/young adult and the researcher presenting the form. The eAssent gives subjects the option to download a copy of the signed form. If a participant refuses or is unable to eAssent but is still interested in participating, a physical assent will be collected by the study team at the next inperson visit to the bariatric surgery center.

C. Study Design and Research Methods

Figure 1. Study Design

The pharmacotherapy group will receive oral phentermine and immediate release topiramate in combination, up-titrated to goal doses of 16mg and 100mg, respectively over 4 weeks*, then maintained at this dose for 8 additional weeks. Topiramate is gradually down-titrated during weeks 13 and 14 to prevent possible discontinuation symptoms.

Dosing Schedule^{†,§}

Uptitration:

- Week 1: 4mg phentermine + 25mg immediate release topiramate
- Week 2: 8mg phentermine + 50mg immediate release topiramate
- Week 3: 12mg phentermine + 75mg immediate release topiramate

Goal Dose:

- Weeks 4-12: 16mg phentermine + 100mg immediate release topiramate **Discontinuation (at study Visit 4)**:
- Week 13: Discontinue Phentermine + Decrease topiramate to 50mg
- Week 14: Decrease topiramate to 25mg for 7 days, then discontinue
- (*) Participants who do not tolerate goal doses will be maintained at the highest tolerated dose. (§) Per existing literature³⁴ and discussion with pharmacy, participants with moderate hepatic impairment (ALT >3x ULN but <10x ULN on two consecutive measures outside of acute illness, and no evidence of hepatic synthetic dysfunction), will follow the same dosing schedule, with doses reduced as needed

based on side effects (See Procedure for Study Drug Dose Reduction/Discontinuation).

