PI	Board Certified in Internal Medicine and Pediatrics; Assistant Professor in Pediatrics, Section of Nutrition with specialized training in pediatric anti-obesity pharmacotherapy; Primary author of Children's Hospital Colorado's Lifestyle Medicine clinical protocols for anti-obesity pharmacotherapy.	Monthly	Yes	Within 5 days of any SAE and monthly for all other AEs
Medical/Safety Officer	Endocrinology faculty member with expertise in pediatric clinical trials	Every 3 months	Yes	Every 6 months
Data and Safety Monitoring Board (DSMB)	Safety Officer (above) + 2 additional faculty with clinical and clinical trial expertise in using anti-obesity pharmacotherapy across the age range studied	Every 6 months	Yes	Every 6 months

A three-member Data and Safety Monitoring board, including a primary Safety Officer, who are independent of the study personnel, have been appointed to this study. Like the study staff, they will be blinded to participants' randomized treatment assignments.

The Safety Officer will:

- 1) Approve criteria for modifying or discontinuing study drugs for individual participants
- 2) Review data generated by the study, including study safety events (SAEs) every 3 months for the duration of the study.

The three-member Data and Safety Monitoring Board will:

- 1) Evaluate the progress of the trial, including periodic assessments of recruitment, screen failures, enrollment, and retention
- 2) Report on the safety and progress of the study every 6 months
- 3) Consider the impact of new or relevant information such as scientific or therapeutic developments (provided by the PI) that may have an impact on the safety or scientific integrity of the study.
- 4) Determine whether the overall integrity and conduct of the study remain acceptable

- 5) Based on these responsibilities/functions, the DSMB will act in an advisory capacity and recommend one of the following actions to the PI ([name]) every 6 months:
 - A) Continue the study according to the protocol and any related amendments.
 - B) Modify the study protocol. Modifications may include, but are not limited to, changes in inclusion/exclusion criteria, frequency/mechanism of safety monitoring, alterations in study procedures, and changes in duration of observation and follow-up.
 - C) Discontinue the study (with provisions for organized discontinuation in accordance with safe medical practice).

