- **5. Will any formal interim analysis be performed?:** Interim assessments of feasibility, acceptability, and safety per above will be performed, but there will be no formal interim analysis for this 12-month study.
- **6. Are there defined** participant **discontinuation criteria?**: There are no *participant* discontinuation criteria. However, there are defined *drug* discontinuation criteria as follows:
 - a) Development of an anaphylactic allergic reaction, pulmonary hypertension, evidence of new valvular heart disease, uncontrolled systemic hypertension, new arrhythmia (including persistent tachycardia), severe anxiety unresponsive to dose decrease, psychiatric disorder that cannot be adequately treated with psycho- and/or pharmacotherapy at the discretion of the study's clinical psychologist, serotonin syndrome, or pregnancy during the pharmacotherapy intervention will lead to discontinuation of phentermine.
 - b) Development of an anaphylactic allergic reaction, nephrolithiasis, severe, persistent cognitive difficulties, psychiatric disorder that cannot be adequately treated with psychoand/or pharmacotherapy at the discretion of the study's clinical psychologist, new acute myopia or secondary angle closure glaucoma, severe metabolic acidosis, hyperammonemia with encephalopathy, or pregnancy during the pharmacotherapy intervention will lead to discontinuation of topiramate.
 - c) If one medication is stopped secondary to the criteria above, the participant, if in agreement, will be continued on the other medication as monotherapy.
 - d) With consent, participants for whom one or both medications are stopped will continue to be followed according to the proposed study timeline.

7. How will the PI/research team determine if an adverse event (AE) is related to either of the study drugs?

Relatedness will be defined according to the National Institutes of Health National Institute on Aging Data Safety and Monitoring Plan Toolkit template (https://www.nia.nih.gov/research/dgcg/clinical-research-study-investigators-toolbox/data-and-safety-monitoring) as follows:

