- There will be a screening visit at 6, 9, or 12 months postoperatively. Eligible participants will be consented at this visit, and will be asked to come to campus ~1 week later for study visit 1. Enrollment and Visit 1 cannot be combined because it is unrealistic to screen, consent, randomize, obtain study drug, and complete additional measures after an already lengthy clinical appointment.
- The Children's Hospital Colorado Lifestyle Medicine weight management program's clinical protocols for anti-obesity pharmacotherapy require monthly clinic visits for the first three months after initiation for monitoring of effects and side effects. The proposed study protocol follows this standard.

Data Collection Tools (See Table 3. below for Schedule of Measures)

- a) Sociodemographic characteristics: age, sex, race/ethnicity, insurance, highest level of primary caregiver's education, household size and income, government-based assistance, and presence/absence of food insecurity will be obtained from the medical record and the Demographics Form.
- b) Feasibility of protocol implementation: rates of recruitment, enrollment, randomization, and dropout
- c) Study medication adherence & tolerability: assessed by 1) Questionnaire: description/dose/start date of medications, missed doses, and checklists of: effects, adverse effects, and evidence-based barriers to adherence^{51,52}; 2) Pill counts; 3) Urine amphetamine screen
- d) Self-reported changes to all non-study medications: name/dose, interim changes
- e) Patient/family satisfaction questionnaire will assess: reasons for participation, experience during study visits, satisfaction with the effect of the study medication/placebo, ease of communication with study staff, and time burden/inconvenience
- f) Biological outcome and safety measures: Weight, height, heart rate (HR), BP, basic metabolic panel, lipids, ALT, HbA1c, and pregnancy test
- g) Optional Biobanking: Gold top (serum-3.5mL blood), Purple top (EDTA-4mL whole blood), Green top (heparinized plasma-4mL blood), and Urine (volume that remains after the urine pregnancy test for females and a separate urine collection for males) will be collected with participant assent/consent for future research questions.
- h) 3-day dietary record: Participants will complete a dietary record on 3 consecutive days (2 weekday, 1 weekend day) based on standardized protocols for dietary assessment.⁵³

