Route of Data Collection: To reduce in-person time on campus for participants, components of Study Visits 1-4 will be collected remotely (designated by superscript "R" in Table 3 below) either via secure video call or telephone call (with questionnaires emailed) in the participant's/guardian's preferred language within the same week and ideally on the same day as the study visit. These measures will be conducted remotely unless it is not possible or places an undue burden on the participant to do so (e.g. participant does not have a reliable internet connection or has a limited phone data plan that incurs significant charges). Pill count will require a video connection. All other measures require in-person collection/administration to appropriately collect outcome/safety data.

Table 3. Schedule of Measures

"X"= Study specific "O"= Standard of Care #= Bariatric Clinic or CHCO CTRC ‡= + Adult CTRC or CHCO Radiology/CTRC R= can be delivered remotely	SCREENING/ ENROLLMENT# 6-12 mo post- op	STUDY VISIT 1#,‡ ~1wk after Enrollment	STUDY VISIT 2# 4wks after Visit 1	STUDY VISIT 3# 4 wks after Visit 2	STUDY VISIT 4#,‡ 4 wks after Visit 3
Review of Inclusion/Exclusion criteria	Х				
Echocardiogram (ONLY for those with Hypertension or Severe OSA with poor PAP adherence IF not obtained in the prior 6 months)	0				
Demographics Form		X ^R			
Feasibility of protocol implementation (e.g. enrollment rates, dropout rates)	х	х	X	х	X
Study medication adherence & tolerability- Study Med Form			X ^R	X ^R	X ^R
Study medication adherence- (pill count)- Study Med Form			X ^R	X ^R	X ^R
Study medication adherence (urine amphetamine screen)		X	X	X	X
Review of all non-study medications (self-report)	Х	X ^R	X ^R	XR	X ^R
Patient/family satisfaction survey					X ^R
Weight, Height, Temperature, HR, BP; Review of Systems; Physical exam		X	Х	X	X
Urine pregnancy test	X	X	X	X	X
Lipid panel, ALT, HbA1c	Х				Х
Basic metabolic panel	Х		Х		X
Optional Biobanking	Х		Х		X
3-day diet record review		X ^R			X ^R
Previous Day Physical Activity Recall (PDPAR)		X ^R			X ^R

IWQOL-Kids (≤19yo)/-Lite (≥ 20yo) & Parent Report		X ^R			X ^R
PedsQL (general health-related quality of life)		X ^R			X ^R
CES-D (Depression Screen)	0	X	X	Χ	X
C-SSRS (Suicide Screen)	X	X	X	Х	X
Resting metabolic rate		X			X
DEXA-3 site		X			Х
Clinical Intervention/Translation Core: Eating behavior questionnaires (VAS, TFEQ, EAH)		X ^R	X ^R	X ^R	X ^R

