Planned analyses: Descriptive statistics will characterize the study population. Independent samples t-tests will be performed for continuous variables and chi-square for categorical variables to determine statistically significant differences between experimental and control groups. Aim 1: Feasibility of acceptability (adherence, tolerability, and satisfaction) will be descriptively assessed using differences in proportions between experimental and control groups. Feasibility of protocol implementation will be established by determining the proportions (rates) of recruitment, enrollment, randomization, and dropout. Aims 2,3: Estimated means and variability of continuous health outcome variables (e.g. % change in weight) and intra- and intersubject variability of repeated measures (e.g. loss of control eating) will be graphically presented and visually compared for experimental vs. control groups, as this aim is not powered to run inferential statistics.

G. Summarize Knowledge to be Gained:

The goal of this study is to establish the feasibility and initial efficacy of two common anti-obesity medications for adolescents who require additional risk reduction following bariatric surgery.

Adolescents with severe obesity who don't achieve optimal weight loss and co-morbidity improvement after bariatric surgery have few evidence-based treatment options to mitigate significant health risks through the remainder of adulthood. This study has the potential for substantial impact regardless of results, given that anti-obesity medications are currently being used in the post bariatric surgery setting without an evidence base. A recent international pediatric obesity webinar (4/2019) with contributors from leading adolescent bariatric surgery centers strongly expressed need and enthusiasm for studying the role of pharmacotherapy after surgery. Our center's volume, interdisciplinary expertise, and existing IND to study these medications in this setting sets us apart as the best positioned adolescent bariatric surgery center to carry out this initial pilot, with high potential for a subsequent larger multi-site RCT to evaluate safety and efficacy, mechanism of action, and predictors of response.

H. References:

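### The urine amphetamine screen cannot show adherence on placebo, so the planned between-arm adherence comparison should exclude it, and the plan should say who receives its on-treatment results

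*Combined protocol and SAP*

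**What the plan says.** Section IV.A lists adherence as part of acceptability under Primary Aim 1, measured by "Self-report by questionnaire, pill counts and urine amphetamine testing". The Data Collection Tools list in Section IV.D, item c, repeats this: after the questionnaire come "2) Pill counts; 3) Urine amphetamine screen". Table 3 has a row that begins "Study medication adherence (urine amphetamine screen", marked at Visits 1, 2, 3 and 4 and not limited to one arm.

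For the Aim 1 analysis, Section IV.F puts adherence, tolerability and satisfaction together under acceptability, which "will be descriptively assessed using differences in proportions between experimental and control groups". It makes no exception for the urine result. It does not say how a negative screen on placebo is scored, or how the three adherence measures are combined.

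On treatment, Section IV.C states: "The pharmacotherapy group will receive oral phentermine and immediate release topiramate in combination". The comparison is with placebo: Section IV.B randomizes 1:1, seven per arm, to pharmacotherapy with standard of care "or placebo + SOC in double-blind fashion". Item 4 of the Data and Safety Monitoring Plan (DSMP) says of the safety board members: "Like the study staff, they will be blinded to" treatment assignments. Item 5 adds: "Interim assessments of feasibility, acceptability, and safety per above will be performed". The visible text does not say who receives the urine results.

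**The concern.** An adherence measure can be compared between arms only if it means the same thing in both. A tablet count or a report of missed doses does. A urine test for the active ingredient does not: on placebo there is nothing for it to find, so perfect adherence and no adherence look alike. Applied to this screen, the Section IV.F comparison mostly measures which arm received phentermine, and it would show an adherence gap where none exists. Adherence is a primary-aim outcome of a pilot intended to shape a larger trial, so a false gap could mislead that planning.

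The second issue is separate and conditional. The same property makes the screen a marker of assignment. If Visit 2 to 4 results reached the study team, knowledge of the arm could influence the staff assessment of adverse effects (Section IV.A) and the judgement of relatedness (DSMP item 7). The interim assessments in DSMP item 5 cover acceptability, which Section IV.F defines to include adherence, and they do not set the urine result apart.

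**Working it through.** The documents state no figure for adherence or for the screen, so there is no plan figure to reproduce.

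**Inputs from the documents.** Allocation is 1:1 with 7 per arm (Section IV.B), and the minimum is 5 per arm (Section IV.F). Phentermine is given in the active arm only (Section IV.C). Screens are at Visits 1 to 4 (Table 3). Study drug starts at Visit 1: the calls that the DSMP sets at 1, 2 and 3 weeks after drug start are set in the call schedule at 1, 2 and 3 weeks after Visit 1. The Visit 1 screen is therefore read as pre-drug, and Visits 2 to 4 as on treatment.

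**Assumed inputs (not in the documents).** True adherence a, equal in both arms; s, the chance of a positive screen in an adherent active participant; f, the background positive rate in everyone else.

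**Formulas.**
- Active-arm positivity: p = a × s + (1 − a) × f. Placebo positivity: f.
- Difference under equal adherence: p − f = a × (s − f). It is zero only if a = 0 or s = f. In the second case the screen measures adherence in neither arm.
- With prior 0.5 from 1:1 allocation, P(active | positive) = p / (p + f).
- P(placebo | negative) = (1 − f) / [(1 − f) + (1 − p)].

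**Results at a = 0.8.**

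| s | f | p | Difference (points) | P(active, given positive) | P(placebo, given negative) |
|---|---|---|---|---|---|
| 1 | 0 | 0.80 | 80 | 1.00 | 1/1.20 = 0.83 |
| 0.6 | 0 | 0.48 | 48 | 1.00 | 1/1.52 = 0.66 |
| 1 | 0.05 | 0.81 | 76 | 0.81/0.86 = 0.94 | 0.95/1.14 = 0.83 |
| 0.6 | 0.05 | 0.49 | 44 | 0.49/0.54 = 0.91 | 0.95/1.46 = 0.65 |
| 0.6 | 0.10 | 0.50 | 40 | 0.50/0.60 = 0.83 | 0.90/1.40 = 0.64 |
| 0.2 | 0 | 0.16 | 16 | 1.00 | 1/1.84 = 0.54 |
| 0.2 | 0.05 | 0.17 | 12 | 0.17/0.22 = 0.77 | 0.95/1.78 = 0.53 |

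With no false positives and s of 0.6 to 1, that is 3.4 to 5.6 positives expected among 7 active participants (7 × 0.48 and 7 × 0.80) against none among 7 on placebo.

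**Wider range.** For a of 0.6 to 1, s of 0.5 to 1 and f of 0 to 0.10, the difference runs from 0.6 × (0.5 − 0.10) = 24 points to 1 × (1 − 0) = 100 points.

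**Chance that it shows in a sample this small.** From exact binomial sums at a = 0.8, the probability that the active arm has more positives than placebo at a single visit is:
- s = 0.9, f = 0: above 0.99 at 7 per arm and at 5 per arm;
- s = 0.7, f = 0.05: 0.98 at 7 per arm, 0.96 at 5;
- s = 0.5, f = 0.10: 0.88 at 7 per arm, 0.81 at 5.

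**Reading one participant's results.** A change from negative at Visit 1 to positive on treatment points to active drug. A negative does not identify placebo: it may also mean missed doses, non-detection, or phentermine stopped with topiramate continued, which DSMP item 6c allows.

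**The case against.** The strongest reply is that Section IV.F speaks of adherence as a whole. It never says that urine positivity will be compared between arms, or that a negative on placebo counts as non-adherence, and a sensible analyst would do neither. It is true that the role of the screen is unspecified, so its effect on an overall adherence figure cannot be determined. But the only analysis rule given for adherence covers this measure without exception, so following the text as written produces the spurious gap.

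A second reply is that the size is all assumption: the documents give no adherence, sensitivity or false-positive rate, and do not say that the screen detects phentermine. That also stands. Detection above background is implied only by the screen's use as an adherence measure, and with poor detection the gap is small.

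A third reply is that this is a descriptive pilot with two sound adherence measures left. A reader might infer that the whole primary-aim adherence result is invalid. The documents do not support that. Pill count and self-report mean the same in both arms. Recruitment, enrollment, randomization and dropout rates are untouched. Hypothesis 1 rests on enrollment, visit completion and satisfaction, not on the urine result. No type I error claim is involved.

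A reader might also infer that the trial is unblinded. The documents do not support that either. Sections IV.B and IV.D state the blinding, and no passage says that results are released to staff. Routing may be set in laboratory or pharmacy instructions not reproduced here, and the progress items listed for the board are recruitment, screen failures, enrollment and retention. What remains is that a general statement of blinding is not a handling rule for a test that can reveal assignment.

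**Conclusion.** The point holds for one of the three adherence measures and should be fixed. The screen cannot register adherence on placebo, and the stated between-arm comparison is not meaningful for it. The direction, higher positivity on active drug, needs only that s exceeds f and that some drug is taken. The size rests on assumed inputs: tens of percentage points if detection is moderate to good, little more than ten if it is poor.

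The blinding issue is a conditional risk. If on-treatment results reached staff, a single positive would imply active drug with probability 0.91 to 1.00 at s of 0.6 to 1 and f of 0 to 5%, and about 0.77 to 0.83 in the less favourable cases with false positives. A single negative would be only weakly informative: 0.65 to 0.83 over the first range, and down to 0.53 at s = 0.2, f = 0.05. These figures assume a = 0.8 and 1:1 allocation.

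**What to change.** 1. In Section IV.F, base the between-arm adherence comparison on pill count and self-report.
2. Report urine positivity as corroboration of phentermine intake (not topiramate intake) within the active arm only. Describe placebo-arm positives as possible off-study use or false positives, not as adherence.
3. As a safeguard for the stated blinding, keep testing both arms but withhold Visit 2 to 4 results from the study team, participants and the blinded board until database lock, including in the interim acceptability assessments. The pre-drug Visit 1 result need not be withheld.
4. As a precaution, confirm that the extra $50 at Visit 4 for meeting adherence targets (Section IV.E) does not depend on the urine result. The text does not name the measure used; if the screen counted, a fully adherent placebo participant could miss the payment.

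The cost is a few sentences in the protocol and a reporting instruction to the laboratory or pharmacy, with no added visit or procedure. The downside is that staff lose the screen as a real-time adherence prompt.
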